4.5.3.1 NRS Score Descriptions

For the purposes of the questions below, the target knee is defined as the knee studied in this trial. Pain in the knee relates to any knee symptom the patient may experience for example pain or aching.

The scale ranges for NRS pain scores range from 0 indicating —“no pain“, to 10 indicating —“pain as bad as it could be“. The NRS scales will be used to assess for:

- 1) NRS question 1: NRSPTO. On average, how would you rate the overall pain severity in your target knee over the last week (7 days)?
- 2) NRS question 2: NRSPAINW. How would you rate your worst pain severity in your target knee over the last week (7 days)?

PAREXEL International Statistical Analysis Plan

Medivir
Protocol: MIV-711-202

Final 1.0
16 January 2018

- 3) NRS question 3: NRSPAINS. On average, how would you rate the overall pain severity in your other knee over the last week (7 days)?
- 4) NRS question 4: NRSACT. Over the last week (7 days), how active do you think your target knee arthritis has been?
- 5) NRS question 5: NRSSAT. Over the last week (7 days), how satisfied have you been with your target knee function?

For purposes of this SAP NRS question 4 refers to the patients “Global Assessment Score”.

4.5.3.2 ICOAP Score Descriptions

Intermittent and constant osteoarthritis pain (ICOAP): an 11-item tool designed to assess constant and intermittent pain. Higher scores indicate worse constant and intermittent pain. The items assessed include:

- IP1- How intense has constant knee pain been
- IP2-Constant knee pain affecting sleep
- IP3-Constant knee pain - quality of life
- IP4-Frustrated by your constant knee pain
- IP5-Upset by your constant knee pain
- IP6-Intensity of pain that comes and goes
- IP7-Frequency pain that comes and goes
- IP8-Pain comes and goes affecting sleep
- IP9-Pain comes and goes quality of life
- IP10-Frustration pain that comes and goes
- IP11-Upset pain that comes and goes

4.5.3.3 WOMAC Score Descriptions

Western Ontario and McMaster Universities Osteoarthritis Index (WOMAC) 3.1: a 24-item OA - specific, tri-dimensional self-administered questionnaire, for assessing health status and health outcomes in OA of the knee. Using an 11-box NRS scale, higher scores indicate worse pain, stiffness and physical function. Items assessed include:

- WOMAC1-Pain - walking on a flat surface
- WOMAC2-Pain - going up or down stairs
- WOMAC3-Pain - at night while in bed

PAREXEL International Statistical Analysis Plan

Medivir
Protocol: MIV-711-202

Final 1.0
16 January 2018

- WOMAC4-Pain - sitting or lying down
- WOMAC5-Pain - while standing
- WOMAC6-Stiffness after first woke up in morning
- WOMAC7-Stiffness sitting or lying down
- WOMAC8-Difficulty - When going down the stairs
- WOMAC9-Difficulty - When going up the stairs
- WOMAC10-Difficulty - Getting up from a sitting
- WOMAC11-Difficulty - While standing
- WOMAC12-Difficulty - When bending to the floor
- WOMAC13-Difficulty - Walking on a flat surface
- WOMAC14-Difficulty - Getting in or out of a car
- WOMAC15-Difficulty - While going shopping
- WOMAC16-Difficulty - When putting on your socks
- WOMAC17-Difficulty - When getting out of bed
- WOMAC18-Difficulty - When taking off your socks
- WOMAC19-Difficulty - While lying in bed
- WOMAC20-Difficulty - Getting in or out of bath
- WOMAC21-Difficulty - While sitting
- WOMAC22-Difficulty - Getting on or off toilet
- WOMAC23-Difficulty - Performing heavy duties
- WOMAC24-Difficulty - Performing light duties

4.5.3.4 OARSI OMERACT Score Descriptions

OARSI-OMERACT Responder index [2, 3] will be calculated using the WOMAC pain and function subscales and the patient's global assessment score as described in sections 4.5.3.1 and 4.5.3.3. A responder will be defined as any subject that satisfies one of the following two overall conditions:

CASE 1. Improvement in pain or function $\geq 50\%$ and absolute change ≥ 20

CASE 2. Improvement in at least two of the following conditions:

1. pain $\geq 20\%$ and absolute change ≥ 10
2. function $\geq 20\%$ and absolute change ≥ 10
3. patients' global assessment $\geq 20\%$ and absolute change ≥ 10

Higher scores indicate worse pain, stiffness and physical function so that an "improvement" is only concerned with negative changes (or decreases) from baseline. Positive increases in scores relative to baseline suggest a worsening of pain (scores increasing over time suggests pain is increasing in severity over time).

PAREXEL International Statistical Analysis Plan

Medivir
Protocol: MIV-711-202

Final 1.0
16 January 2018

4.5.3.5 Global Improvement Score Descriptions

Global improvements in knee problem, knee pain and knee function (Ability to use knee), recorded on a 6-point Likert scale at visit 4 and visit 5: (completely better, much better, better, no change, worse, much worse).

4.5.3.6 Quality of Life

At visit 5: EuroQol -5 Dimensions (EQ-5D-5L) - a generic measure of self-reported health status. Items assessed include:

- Usual Activities
- Anxiety/Depression
- Self-Care
- Pain/Discomfort
- Mobility
- Health Rating

4.5.3.7 Brief Medication Questionnaire

The Brief Medication Questionnaire is a self-reported measure for the use of concomitant medication and will be administered at visit 4 and visit 5. Items assessed include:

- How much did you take each time
- How many days did you take it
- The dosage times are inconvenient
- How many times per day did you take it
- It is hard to get my refill on time
- How many times did you miss taking it
- It is hard to open the container
- Hard to read the print on the container
- For what reason were you taking it
- It is hard to remember all doses
- Stop taking meds since the start of the study or since the previous visit
- Medication Name

4.5.3.8 E-Diary Assessment of NRS and Analgesic Use

In an e-diary format, a patient knee pain diary (NRS) and analgesia questionnaire will be completed daily every 12 hours (AM, PM) during two 2-week periods prior to visit 4 and visit 5. The assessments in the e-diary comprise:

PAREXEL International Statistical Analysis Plan

Medivir
Protocol: MIV-711-202

Final 1.0
16 January 2018

- Average overall knee pain severity in the target knee over the past 12 h (0 -10 NRS)
- Adherence to usual analgesics regimen:
 - Has patient taken any pain medication over last 12 hours? (Yes, No).
 - Classify your pain medication usage over the last 12 hours: (More than normal, Normal, Less than normal)
- Intake of IMP (note: the e-diary device is kept by the patients for the full duration of the study, intake of IMP will be registered daily throughout the study)

4.5.4 Other Efficacy Parameters – Biomarkers, Imaging, Pharmacokinetics

Biomarkers

Blood and urine samples will be taken at Visits 2, 4, 5 and 6, for analysis of exploratory bone and cartilage markers of relevance for OA disease, such as CTX-I, PINP, BSAP and TRAP5b in serum and NTX-I, CTX-I, alphaCTX-I and CTX-II in urine.

Imaging

The imaging assessment will be derived in the source as change from baseline to Visit 5 in the current study as a calculated compound index of MRI bone area and cartilage thickness.

Pharmacokinetics

The analysis of the pharmacokinetics and metabolism of MIV-711 and the relationship to patient factors and concomitant medications will be conducted by the sponsor and described in a separate report. The PK analysis will not be considered in this SAP.

4.6 Analysis Populations

The analysis populations that will be used in the analyses are defined in Section 4.6.1, Section 4.6.2 and Section 4.6.3 below. Note that the analysis populations Population A and Population B as defined in the CSP are not considered statistical analysis populations but defined to indicate the two different treatment groups. No amendment to the CSP will be done, but the discrepancy between the CSP and the SAP regarding the analysis populations will be clarified in the section “Changes to planned analysis” in the CSR.

PAREXEL International Statistical Analysis Plan

Medivir
Protocol: MIV-711-202

Final 1.0
16 January 2018

4.6.1 Intent-to-Treat Population (ITT)

All patients enrolled to the study MIV-711-202 and receives at least one dose of the IMP.

4.6.2 Per Protocol Population (PPS)

The patients in the ITT population without any major protocol deviations as described in section 5. A patient that discontinuates from the study will typically be part of the ITT population but will not be included in the PPS population.

4.6.3 Safety Analysis Population (SAF)

The safety analysis population will be the same as the ITT population.

5. Protocol Deviations

Deviations from the protocol including violations of inclusion/exclusion criteria will be assessed as “minor” or “major” in cooperation with the sponsor. Major deviations from the protocol will lead to the exclusion of a patient from the Per Protocol Set (PPS). Deviations will be defined prior to data base hard lock.

The following criteria will be used to exclude a patient from an analysis set:

- Incorrect diagnosis
- Any of the prohibited interventions/injuries for the target knee
- Missing more than 7 doses of MIV-711
- Discontinuation from the study

Note: this is not an exhaustive list of deviations, these are only the deviations specified per protocol. The discussion during the data review meeting post data base soft lock will review all deviations collected at each site and it will be decided to which analysis set each patient belongs.

6. General Considerations for Data Presentations

In this study IMP refers to any amount of the treatments defined in section 3.5, regardless of the time or period of administration.

Data for all patients enrolled in study MIV-711-202 who receives at least one dose of IMP will be presented in the data listings.

PAREXEL International Statistical Analysis Plan

Medivir
Protocol: MIV-711-202

Final 1.0
16 January 2018

A patient who is enrolled in study MIV-711-202 but does not receive IMP will be included in those data listings for which they have data but will be excluded from all data summaries. Data summaries will only include those patients that receive IMP.

For those listings or data summaries where baseline and change from baseline measurements will be presented, unless stated otherwise, the baseline assessment to be used for calculating change from baseline will be the last valid assessment prior to first dose of 200 mg MIV-711. Note that the change from baseline will be calculated also for visits prior to the baseline visit, not only for visits succeeding the baseline visit.

Data from both studies for patients enrolled in study MIV-711-202 will be included in the data listings, tables and figures, as appropriate.

All pre- and post-dose assessments including unscheduled assessments will be included in the data listings. For unscheduled assessments collected pre-dose, the last assessment taken for a time point will be used in the data summaries (summary tables, figures, and statistical analysis); for all post-dose time points, the original assessment for any given time point will be used in the data summaries (summary tables, figures, and statistical analysis).

Descriptive statistics for observed values and derived change from baseline values will be tabulated by visit and study group. Continuous variables will be summarized by study group and visit, as appropriate, using descriptive statistics including: number of observations (n), mean (arithmetic), median, standard deviation (SD), minimum, and maximum. Frequencies and percentages will be used for summarizing discrete (categorical) data by study group and visit, as appropriate. The denominator used when calculating percentages will be the number of patients assessed at a particular combination of study group and study visit, as appropriate.

Safety and efficacy data that are reported as missing will be excluded from all descriptive and non-descriptive data analysis. There will be no imputation of any data. Observations that might be considered spurious (extreme relative to the majority of the data) will not be altered or removed from any presentation of the data, including the calculation of summary statistics (means, medians, etc.), unless approved by the sponsor.

For data listings, all raw data will be reported/displayed exactly as provided. For summaries of quantitative safety data, the minimum and maximum value will be reported exactly as the raw data are reported; measures of central tendency (means, medians) will be reported to one more decimal place than the raw data; measures of variance (SD) will be reported to two more decimal places than the raw data.

Unless stated otherwise there will be no adjustment for multiple comparisons.

PAREXEL International Statistical Analysis Plan

Medivir
Protocol: MIV-711-202

Final 1.0
16 January 2018

In all data presentations ‘Treatment’ will be defined as 200 mg MIV-711. Listings will include all patients and will be sorted by patient number and time point (where applicable). All derived data used in a data summary or statistical analysis will be listed.

6.1 Software

All statistical analyses will be performed using Statistical Analysis Software (SAS[®]) (SAS[®] Institute Inc., Cary, North Carolina, United States of America [USA]) Version 9.2 or higher.

7. Patient and Treatment Information

7.1 Patient Disposition

The completion status, date of completion or discontinuation, the reason for discontinuation, and the study day of withdrawal will be listed. The number of patients enrolled and the frequency and percentage of patients completing the study, patients withdrawing early, and primary reason for withdrawal will be summarized. Also included in this summary will be the numbers of patients in each of the analysis populations: ITT, PPS, SAF.

7.2 Patients Excluded from Analysis Populations

Each patient excluded from one of the analysis populations will be listed along with the reason for their exclusion.

7.3 Eligibility Criteria

All enrolled patients who did not meet an inclusion criterion and all enrolled patients who met an exclusion criterion will be listed.

7.4 Exclusion Tests

Results of the exclusion tests will be listed. These will include laboratory tests performed prior to dosing for: FSH testing, and urine drug screen.

7.5 Protocol Deviations

All reported protocol deviations will be listed.

PAREXEL International Statistical Analysis Plan

Medivir
Protocol: MIV-711-202

Final 1.0
16 January 2018

7.6 Demographic Data

Demographic and baseline characteristics will be evaluated for Group A and Group B. Demographic information will be listed. Descriptive statistics will be obtained for the continuous variables: height, age, BMI, and body weight and presented overall. Frequencies and percentage of patients will be tabulated for the categorical variables ethnicity, race, and gender.

Patient height will be obtained from MIV-711-201 study.

7.7 Medical History

Medical and surgical history data recorded prior to dosing will be listed for each patient. Medical history will be coded using the MedDRA (Version 18.1).

Only those body systems where a condition or abnormality has been reported will be listed.

Any medical history data with start date after visit 2 in the MIV-711-201 study will be flagged in the medical history data listing. This data was collected as adverse event data during the MIV-711-201 study.

AEs from the MIV-711-201 study are recorded as medical history in the MIV-711-202 study. Any medical history data with start date after visit 2 in the MIV-711-201 study (i.e AEs) and which were ongoing at visit 1 in the MIV-711-202 study will be flagged in the medical history data listing.

Flagged medical history items will be summarized by system organ class, preferred term, and treatment.

7.8 Prior and Concomitant Medication

Prior and concomitant medications will be coded using WHO Drug (September 2015 version). These medications will be classified by Anatomical Therapeutic Chemical (ATC) categories.

Prior and Concomitant Medications will be listed by patient.

Summary tables of the number of patients and percentage of patients by group and ATC classification will be provided for prior and concomitant medications. ATC level 1 and ATC level 3 will be used.

PAREXEL International Statistical Analysis Plan

Medivir
Protocol: MIV-711-202

Final 1.0
16 January 2018

Relevant prior and concomitant medication from MIV-711-201 will be recorded as prior medication in the MIV-711-202 study. Two indicative variables/flags will be added to the data listings/database:

1. Prior medications with start date after visit 2 in the MIV-711-201 study will be flagged in the data listing.
2. Prior medications ongoing after visit 1 in the MIV-711-202 study will be flagged in the data listing.

Flagged prior medications will be summarized by ATC level 1 and ATC level 3, and treatment group.

7.9 Dose Administration

Information collected per the dose administration CRF will be listed including patient number, visit, date and time of administration, number of capsules dispensed and number of capsules returned.

The number and percentage of patients who received IMP will be summarized for each on site visit. Descriptive statistics will be used to summarize drug accountability as the number of capsules returned for each on site study visit by treatment.

Compliance will be derived as the number of days patient were exposed to IMP. 100% compliance will be considered for dosing during the period Visit 2 to Visit 5. The number of capsules used will be derived as the number of capsules dispensed minus the number of capsules returned. Subjects with less than 100% compliance will be identified among those who have results for “Reason not all unused Capsules returned”. The compliance will not be calculated for withdrawn patients, as the date of the last IMP dose taken is not captured in the database.

8. Pharmacodynamic Analysis – Efficacy

The baseline will be the last valid assessment prior to first dose of 200 mg MIV-711, i.e. the baseline visit is defined as

- Visit 2 in study MIV-711-201 for study group A
- Visit 8 in study MIV-711-201 for study group B

The exception is for the biomarkers in study group B, where the baseline visit is defined as visit 2 in the present study (MIV-711-202).

The change from baseline for visit X will be calculated as the (visit X – baseline visit) difference in observed values. Note that the change from baseline will be calculated for all visits in study MIV-711-201 and study MIV-711-202 where the actual endpoint has

PAREXEL International Statistical Analysis Plan

Medivir
Protocol: MIV-711-202

Final 1.0
16 January 2018

been observed, i.e. not only for visits in study MIV-711-202 succeeding the baseline visit.

All efficacy analyses will be made on the ITT population if not stated otherwise.

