#### **6.5 Compliance**

The administration of all medication (including IMP) must be recorded in the appropriate sections of the eCRF. The Investigator is responsible for discussing the treatment compliance with the patient before enrolment in the study. Drug accountability will be performed and compliance of drug accountability will also be discussed with the patient.

Treatment compliance will be analysed via capsule count. More details will be given in the Statistical Analysis Plan (SAP).

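### SAP 7.9 looks for incomplete compliance in the wrong patients and conflicts with the capsule-count ratio in the SAP's own shells

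*SAP*

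**What the plan says.** Protocol 6.5 fixes the measure and leaves the detail to the SAP: "Treatment compliance will be analysed via capsule count".

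SAP 7.9 then makes several statements that do not fit together:

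- "Compliance will be derived as the number of days patient were exposed to IMP". This is a number of days, not a percentage.
- "100% compliance will be considered for dosing during the period Visit 2 to Visit 5".
- "Subjects with less than 100% compliance will be identified among those who have results for" the field giving the reason that not all unused capsules were returned.
- "The number of capsules used will be derived as the number of capsules dispensed minus the number of capsules returned".
- On withdrawals: "The compliance will not be calculated for withdrawn patients, as the date of the last IMP dose taken is not captured in the database".

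The shells do use a ratio. Listing 16.2.5.4 (ITT) defines overall compliance as total capsules used over total days exposed, times 100%. Table 14.1.9 (PPS) summarises planned days of exposure, capsules used and percentage compliance. Neither is restricted to patients with a reason entry, and both omit withdrawn patients.

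SAP 5 lists, among the criteria that exclude a patient from an analysis set, "Missing more than 7 doses of MIV-711". No derivation of missed doses is given.

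**The concern.** Whether a patient has explained some missing capsules says nothing about whether doses were skipped. A patient who skips doses and brings back every leftover has no reason entry, so the 7.9 text does not look at that patient. A patient who takes every dose but loses a few capsules does have an entry and is searched.

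The shells do not settle the matter, because their denominator is described in three ways: planned days (Table 14.1.9), days of actual dose exposure between Visit 2 and Visit 5 (Listing 16.2.5.3) and days exposed (Listing 16.2.5.4). A programmer could follow the SAP faithfully and report quite different percentages for the same patient.

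At stake are the descriptive compliance figures and the information on which the criterion of more than 7 missed doses is applied.

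**Working it through.** The documents state no compliance figure, so there is nothing to reproduce. The check applies each reading of the SAP to the same example patients.

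**Inputs**

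- Treatment days: Visit 2 is Day 1, Visit 5 is Day 182 ± 7 days, and the last dose is taken at Visit 5 (SAP 4.2). Counting both end days gives 182, range 175 to 189.
- One capsule per day (footnote to Listing 16.2.5.3).
- Capsules used = dispensed − returned (SAP 7.9).
- Capsules dispensed: not stated; 200 is assumed. When all unused capsules are returned the number cancels, since used = dispensed − (dispensed − taken) = taken.
- Assumed: the reason field is filled in when unused capsules are missing, and only then.

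**Readings**

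- R1, the 7.9 text: 100% unless there is a reason entry.
- R2, Listing 16.2.5.4 with calendar days from Visit 2 to Visit 5: used / 182 × 100.
- R3, Listing 16.2.5.4 with days actually dosed: used / days dosed × 100.

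**Results at 182 days**

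| Patient | Returned | Used | R1 | R2 | R3 |
|---|---|---|---|---|---|
| 20 missed, all leftovers returned | 200 − 162 = 38 | 162 | no entry, 100% | 162/182 = 89.0% | 162/162 = 100% |
| None missed, 10 capsules lost | 200 − 182 − 10 = 8 | 192 | in the searched group | 192/182 = 105.5% | 192/182 = 105.5% |
| 10 missed, those 10 not returned | 200 − 172 − 10 = 18 | 182 | in the searched group | 182/182 = 100.0% | 182/172 = 105.8% |

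For the first patient the visit window moves R2 only from 155/175 = 88.6% to 169/189 = 89.4%.

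**The per-protocol limit.** On R2 with all leftovers returned, 7 missed doses is 175/182 = 96.2% and 8 is 174/182 = 95.6%. The boundary is a single capsule. R1 and R3 show 100% on both sides of it.

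**The case against.** The strongest reply is that the output specification already does the right thing. Listing 16.2.5.4 and Table 14.1.9 are not limited by the reason field, and on calendar days they show the first example patient at 89.0%. That stands. A reader might infer from 7.9 that such patients go unidentified anywhere in the SAP; the shells do not support that. What remains is a conflict between text and shells, and a denominator that hides the missed doses if read as days actually dosed.

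A reader might also infer that non-adherent patients will stay in the PPS. The documents do not show this. SAP 5 leaves analysis-set membership to a data review meeting after soft lock, and nothing ties the missed-dose criterion to the reason field. Membership could be affected; that it will be is conjecture. Withdrawn patients play no part here, because discontinuation already removes them from the PPS.

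A third tempting inference is that exposure behind the 52-week safety claim is overstated. Safety tables use the SAF, which needs only one dose, and the adverse event percentages divide by patients exposed. Table 14.1.9 covers dosing in MIV-711-202 only. No safety result changes.

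Finally, the e-diary may look like a ready source, since SAP 4.5.3.8 says "intake of IMP will be registered daily throughout the study". But SAP 4.5.3 says the intake item is there to encourage compliance and its data will not be reported, Listing 16.2.6.21 has no column for it, and Protocol 7.4.1 describes diary completion only in two 2-week periods. It cannot be treated as an agreed primary source.

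**Conclusion.** The point holds as a defect of definition. The rule in SAP 7.9 selects the wrong group, contradicts the shells, and leaves the denominator open. For 20 of 182 missed doses with full return of leftovers, the SAP supports either 100% or 89.0%. Counting unreturned capsules as taken can hide missed doses entirely (100% with 10 missed) or push compliance above 100% (105.5% with none missed).

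These examples rest on one capsule a day, 182 treatment days and, where capsules are lost, the assumptions about dispensing and the reason field stated above. How many patients would be affected cannot be known from the documents.

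The reach is limited: descriptive compliance, and possibly PPS membership, which matters mainly for the repeat Imorphics MRI outputs (Tables 14.2.1.4 to 14.2.1.6, Figures 14.2.1.7 to 14.2.1.9). Efficacy analyses default to the ITT population. Separately, Table 14.1.9 is on the PPS, from which patients excluded for missed doses have already gone, so it will flatter compliance even with a sound formula. It is worth correcting because the correction is cheap.

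**What to change.** 1. In SAP 7.9, delete the presumed 100% and the reason-based sentence.
2. Define compliance for all non-withdrawn patients as (dispensed − returned) / (Visit 5 date − Visit 2 date + 1) × 100, and use the same denominator and label in Listings 16.2.5.3 and 16.2.5.4 and Table 14.1.9.
3. Flag patients with unreturned capsules as having an uncertain count, instead of treating those capsules as taken.
4. For the PPS criterion, derive missed doses as (Visit 5 date − Visit 2 date + 1) − (dispensed − returned). For flagged patients this is only a lower bound: above 7 it settles the criterion; otherwise the data review meeting decides and records why.
5. Show the compliance summary on the ITT/SAF as well as the PPS.
6. Use e-diary intake entries only as a supporting source, including for last-dose dates of withdrawn patients, and only after SAP 4.5.3 and 4.5.3.8 have been reconciled and the completeness of the entries checked.

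The cost of items 1 to 5 is SAP wording and a short derivation on capsule counts and visit dates already collected. Item 6 changes a stated SAP decision and is optional. The downside is that reported compliance may fall slightly.

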'Number of actual days exposed to IMP' is the number of days of actual dose exposure from V2 (first dose) to V5 (last dose), since each patient is to receive 1 capsule of dosing per day of dose administration.
Withdrawn patients are not included in this listing.

PAREXEL International SAP Amendment Shells

Medivir
Protocol: MIV-711-202

Final 1.0
16 January 2018

Medivir
Protocol Number: MIV-711-202

Page X of Y

Listing 16.2.5.4
Dose Administration Overall Compliance at Visit 5, ITT Population

Study Group = Group A

Patient MIV- 711-202	Patient MIV- 711-201	Visit	Date of Dose	Total Dispensed Amount (Capsules) [1]	Total Returned Amount (Capsules) [2]	Total Actual Number of Capsules Used	Total Number of Days exposed to IMP	Overall IMP Compliance
----------------------------	----------------------------	-------	--------------------	---	--	---	---	------------------------------

[1] obtained as the total number over visits 2, 4.

[2] obtained as the total number over visits 4, 5.

The 'Total actual number of capsules used' was derived as the 'Total number of capsules dispensed' minus the 'Total number of capsules returned'.
Overall IMP compliance: $(\text{Total actual number of capsules used} / \text{Total number of days exposed to IMP}) \times 100\%$
Withdrawn patients are not included in this listing.

PAREXEL International SAP Amendment Shells

Medivir
Protocol: MIV-711-202

Final 1.0
16 January 2018

Medivir
Protocol Number: MIV-711-202

Page X of Y

Listing 16.2.6.1
Numerical Rating Scale of Knee Pain (One Week Recall)

Study Group = Group A

Patient	Patient	Visit	Date of	Target	Overall	Worst	Overall	Global	Satisfied
MIV-	MIV-711-201		Assessment	Knee	Pain	Pain	Pain	Disease	with
711-202				Used	in	Severity	Severity	Activity	Target
				for NRS	Target	Target	Other		Knee
					Knee	Knee	Knee		Function

PAREXEL International SAP Amendment Shells

Medivir
Protocol: MIV-711-202

Final 1.0
16 January 2018

Medivir
Protocol Number: MIV-711-202

Page X of Y

Listing 16.2.6.2
Numerical Rating Scale of Knee Pain Change From Baseline (One Week Recall)

Study Group = Group A

Patient MIV- 711-202	Patient MIV-711-201	Visit	Date of Assessment	Target Knee Used for NRS	Overall Pain Severity in Target Knee	Worst Pain Severity Target Knee	Overall Pain Severity in Other Knee	Global Disease Activity	Satisfied with Target Knee Function

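### SAP 7.9 looks for patients below 100% compliance in the wrong subset, and conflicts with the compliance formula in the SAP's own listing shells

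*SAP*

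**What the plan says.** Protocol Section 6.5 bases treatment compliance on capsule counts and leaves the details to the SAP. SAP Section 7.9 supplies them in four statements:

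- "Compliance will be derived as the number of days patient were exposed to IMP". No ratio and no denominator are given.
- Full compliance is tied to the dosing period that runs from Visit 2 through Visit 5.
- Capsule use is what was handed out less what came back.
- "Subjects with less than 100% compliance will be identified among those who have results for" the reason-for-non-return field.

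Section 7.9 adds that compliance is not calculated for withdrawn patients, because the date of their last dose is not in the database.

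The shells go further than the text. The footnote to Listing 16.2.5.4 (ITT) defines overall compliance as total capsules used divided by total days exposed, times 100, and leaves out only withdrawn patients. The footnote to Listing 16.2.5.3 says that the number of actual days exposed "is the number of days of actual dose exposure from V2 (first dose) to V5 (last dose), since each patient is to receive 1 capsule" per day. Table 14.1.9 (per-protocol set) shows planned days of exposure, capsules used and overall compliance, with no formula.

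Separately, SAP Section 5 lists "Missing more than 7 doses of MIV-711" among the criteria for excluding a patient from an analysis set.

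**The concern.** The field that Section 7.9 uses to find imperfect compliance is filled when capsules were not brought back. A missed dose has the opposite sign: the capsule stays in the bottle and is returned as surplus. A patient who skips doses and returns every unused capsule gives an accurate count with a visible shortfall, but has no entry in the field and so falls outside the search. The patients inside the search have a count that can overstate intake, because dispensed minus returned treats an unreturned capsule as taken.

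At stake is whether the compliance percentage means the same thing in the text, the listings and the table. No other reported dose record would settle it: SAP Section 4.5.3 says that IMP intake from the e-diary will not be reported. The SAP also gives no derivation of the missed-dose number that the more-than-7 criterion needs.

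**Working it through.** The documents state no compliance figure to reproduce, so the check compares the readings for the same patient.

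**Inputs**

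- Planned doses: once daily for 26 weeks. The study schedule puts Visit 2 at Day 1 and Visit 5 at Day 182, so planned = 182 − 1 + 1 = 182. The ±7-day window at Visit 5 gives 175 to 189.
- Capsules used = dispensed − returned (SAP 7.9).
- Number of missed doses, m: an assumption, varied from 7 to 60. The number dispensed is not stated, but it cancels when all unused capsules are returned, since used is then planned − m.

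**Case 1: all unused capsules returned**

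- Identification rule in 7.9: no non-return reason, so the patient is not identified as below 100%.
- Listing 16.2.5.4 with calendar or planned days: (182 − m)/182 × 100.
- Listing 16.2.5.4 with dosed days only: (182 − m)/(182 − m) × 100 = 100%.

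| Missed (m) | Used | Identified by 7.9 | Ratio, calendar days | Ratio, dosed days | More than 7 missed |
|---|---|---|---|---|---|
| 7 | 175 | no | 96.2% | 100% | no |
| 8 | 174 | no | 95.6% | 100% | yes |
| 14 | 168 | no | 92.3% | 100% | yes |
| 30 | 152 | no | 83.5% | 100% | yes |
| 60 | 122 | no | 67.0% | 100% | yes |

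For 30 missed doses, the visit window moves the calendar-day value from 145/175 = 82.9% to 159/189 = 84.1%.

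**Case 2: 30 doses missed and those 30 capsules not returned**

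Used by count = 152 + 30 = 182, and 182/182 = 100%. The non-return field is filled, so this patient is inside the 7.9 search, yet the count shows no missed dose.

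The two cases show what the field marks: a count that may be too high, not a count that reveals missed doses.

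**Denominator labels side by side**

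- Listing 16.2.5.3: actual days exposed.
- Listing 16.2.5.4: total days exposed.
- Table 14.1.9: total planned days of exposure.

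The first can be read as dosed days and the third cannot. In the 30-dose example the choice is worth 100 − 83.5 = 16.5 percentage points.

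**The case against.** The strongest reply is that the outputs, on their natural reading, give the right answer. The Listing 16.2.5.4 formula covers every non-withdrawn patient and is not limited to those with a non-return reason. Table 14.1.9 uses planned days. Withdrawn patients are left out because their last dose date is missing, and that date matters only if the denominator runs from first to last dose. The statement about 100% from Visit 2 to Visit 5 can be read as defining full compliance rather than as a default value for everyone. On that reading the patient with 30 missed doses appears at 83.5%.

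This stands. A reader might infer that non-adherent completers will be reported as 100% compliant with no chance of detection. The documents do not support that: it requires the 7.9 sentence to override the listing formula, or days exposed to mean dosed days.

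A reader might also infer that such patients stay in the per-protocol set. Nothing ties the more-than-7 criterion to the 7.9 sentence. SAP Section 5 leaves set membership to a data review meeting that considers all site deviations, and dispensed, returned and used capsules are listed by patient.

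The unreturned-capsule case is a limit of any capsule count, the method the protocol chose. It is not an error specific to 7.9.

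The reply does not remove the 7.9 sentence, which names the wrong patients on any reading. Nor does it settle the denominator: the Listing 16.2.5.3 footnote reasons from one capsule per day, so a programmer could count only dosed days and still claim to follow the SAP.

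**Conclusion.** The point holds as a wrong identification rule in SAP 7.9, a conflict between that rule and the Listing 16.2.5.4 formula, and an inconsistently labelled denominator. A patient who missed doses and returned every unused capsule is not identified by the rule, however many doses were missed. The listing formula would show that patient at 95.6% for 8 missed doses and 67.0% for 60, if days are calendar or planned days. If only dosed days are counted, the ratio is 100% whenever all unused capsules are returned.

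These values assume 182 planned doses and chosen numbers of missed doses. The documents do not say how many patients would be affected.

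The reach is limited. Any effect on per-protocol membership depends on what the data review meeting uses. If it does remove patients with more than 7 missed doses, they also leave Table 14.1.9, and the conflict shows mainly in the ITT listings. A reader might take this as undermining the safety results. It does not: the safety set needs only one dose, and its analyses do not use the compliance figure.

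**What to change.** In SAP 7.9, delete the sentence that limits identification to patients with a non-return reason, and state that 100% means one capsule per calendar day from Visit 2 to Visit 5. Then, for every non-withdrawn patient with a Visit 5 count, define:

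- planned doses = Visit 5 date − Visit 2 date + 1
- used = dispensed − returned
- missed = planned − used
- compliance = used/planned × 100

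Use this denominator, under one label, in Listings 16.2.5.3 and 16.2.5.4 and in Table 14.1.9. Keep the non-return reason only as a data-quality flag that the count may overstate intake. Do not add a calculation with unreturned capsules treated as all taken or none taken: the listed fields hold no number of unused capsules not returned, so the second value cannot be computed. Give the missed-dose count to the data review meeting for the existing more-than-7 criterion.

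The cost is a few lines of SAP text and programming on visit dates and capsule counts already collected. Reported compliance may be slightly lower, and a few more patients may leave the per-protocol set.
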